# 9.6.1.4 Secondary Efficacy Endpoint Analyses

The key secondary endpoint will be the proportion of subjects with decline in FVC % predicted ≥10% from Baseline at Week 52 and will be analyzed using a logistic regression model with treatment group and stratified by factors used for stratifying the randomization. The logistic model will provide odds ratio, its 90% CI and p-value for comparing each fipaxalparant (HZN-825) group with the placebo group. Statistical significance for the key secondary endpoint will only be concluded if statistical significance is achieved for the primary efficacy endpoint.

Changes from Baseline in 6MWT, K-BILD, L-IPF, and LCQ scores will be analyzed analogously to the primary efficacy endpoints. Survival analysis will be used for the time-to-event endpoints, including time to the first onset of the composite endpoint and the time to the first hospitalization due to respiratory distress. A Cox proportional hazard model stratified like the previous logistic model with treatment group will provide hazard ratio, its 90% CI and p-value to compare each fipaxalparant (HZN-825) group with the placebo group.

Date: 07 October 2024 IND 154671

# 9.6.1.5 Exploratory Endpoint Analyses

Exploratory endpoints will be summarized at each time point. The statistical methods for comparisons of each dose regimen of fipaxalparant (HZN-825) to placebo will be analogous to the methods for comparisons of primary and secondary efficacy endpoints. Correlation analysis will be used to assess the relationship between the percent change from Baseline in FVC % predicted and the percent change from Baseline in lung fibrosis scores at Week 52.

# 9.6.1.6 Safety and Tolerability Analyses

All subjects who receive at least 1 dose or partial dose of trial drug will be included in safety and tolerability analyses. Subjects who receive treatment other than that to which they were randomized will be included in summaries with the treatment received. Subjects who receive more than 1 treatment will be listed separately and included in summaries with the treatment received most frequently.

The number and percentage of subjects reporting at least 1 TEAE, SAE, AESI, and TEAE resulting in premature discontinuation of trial drug for each unique System Organ Class (SOC) and Preferred Term will be summarized. AE rates (events per patient-year of follow-up during dosing) will also be summarized to account for the different treatment durations. TEAEs and SAEs will also be summarized by severity and relationship to trial drug as assessed by the Investigator. Grade 3 and above TEAEs will also be summarized for each unique SOC and Preferred Term. Orthostatic hypotension is prospectively defined as an AESI and will be summarized separately.

Summary statistics will be used for laboratory values, vital signs, ECG results, and use of concomitant medications.

No inferential statistics are planned for any safety endpoint.

### 9.6.1.7 Pharmacokinetic Analyses

PK data will be analyzed using the PK analysis set. Plasma concentrations of fipaxalparant (HZN-825) will be summarized descriptively, including arithmetic means, standard deviations, geometric means, coefficients of variation, medians, first and third quartiles and ranges by treatment group and by time point. Population PK analysis may be performed.

# 9.6.1.8 Interim Analysis

An interim analysis of the primary efficacy endpoint will be conducted using unblinded data after

This analysis will have 2 potential outcomes:

- If neither dose regimen of fipaxalparant (HZN-825) shows better efficacy compared to placebo with an acceptable safety profile, the trial will be discontinued for futility.
- If 1 or both dose regimens of fipaxalparant (HZN-825) show better efficacy compared to placebo with an acceptable safety profile, the trial will continue with no changes.

Fipaxalparant (HZN-825)

Version 5.0, Amendment 4

Protocol: HZNP-HZN-825-303

Fipaxalparant (HZN-825) Protocol: HZNP-HZN-825-303 Version 5.0, Amendment 4

The futility analysis will not be used to make a positive determination of efficacy to stop the trial.

Conditional power will be used to determine which of the options is chosen, with a conditional power of  $\geq 10\%$  required for at least 1 dose regimen to continue the trial. Other statistics, such as Bayesian statistics, may also be used for the futility analysis and dose selection.

To support the dose selection and as part of the Week 28 unblinded interim analysis, the FVC % predicted change from Baseline at Week 28 will be evaluated in subjects who were randomized with concomitant standard-of-care treatment at Baseline. Approximately 60 subjects in the standard-of-care stratum with 28 weeks of data (approximately 20 subjects per arm) will be included. The positive signal in the FVC % predicted change from Baseline at Week 28 and related results in standard-of-care subjects will support the dose selection and future trial design.

Additionally, safety will be assessed, and an fipaxalparant (HZN-825) dose regimen that has an unacceptable safety profile will be discontinued and subjects assigned to that dose regimen would be assigned to the other dose regimen for the remainder of the trial, if the other dose regimen continues.

At the interim analysis, the IDMC will provide recommendation to select Horizon personnel not involved in the oversight of the trial to facilitate trial continuation and dose selection for future trials. To support decisions on future dose selection and future trial design, a Horizon unblinded team may be established and receive unblinded data and perform ad hoc analyses, as needed. All unblinded data and analysis results made available to the Horizon unblinded team will be archived to allow for any potential post hoc assessments of bias. For additional details, please refer to the IDMC charter and Blinding Maintenance Plan for this trial.

# 9.6.1.9 Multiple Comparisons

The overall statistical level is  $\alpha$ =0.10 (2-sided). Because 2 dose regimens of fipaxalparant (HZN-825) will be compared to placebo, a hierarchical testing procedure will be used for multiple comparisons. Therefore,  $\alpha$ =0.10 (2-sided) will be used in the final analysis. The hierarchical testing procedure will be used for the primary and key secondary endpoint. For the primary endpoint, the BID dose will be tested versus placebo first; if significant, the QD dose will then be tested. If 1 or 2 dose regimens of the primary endpoint are not rejected after completing testing, no further testing will occur. If both fipaxalparant (HZN-825) doses are statistically significantly better than placebo for primary efficacy endpoint, the testing procedure will continue for the key secondary endpoint and will be similar to that performed for the primary endpoint.

Although p-values will be provided for the other secondary and exploratory endpoints, they will not be used for inferential purposes.

#### 9.6.2 Extension Phase

### **9.6.2.1** Endpoints

Two types of Baseline are defined for the Extension Phase:

PRIVATE AND CONFIDENTIAL INFORMATION OF HORIZON THERAPEUTICS IRELAND DAC (A WHOLLY OWNED SUBSIDIARY OF AMGEN INC.)

Page 100 of 153

- OLE Baseline, defined as the latest measurement prior to the first dose of fipaxalparant (HZN-825) in Extension Phase
- Fipaxalparant (HZN-825) Baseline, defined as the latest measurement prior to the first dose of fipaxalparant (HZN-825) in either the Core Phase or the Extension Phase. For subjects who received placebo in the Core Phase, OLE Baseline will be the same as fipaxalparant (HZN-825) Baseline.

# 9.6.2.1.1 Primary Efficacy Endpoint

The primary endpoint is the change from both Baselines in FVC % predicted at Week 104.

### 9.6.2.1.2 Safety and Tolerability Endpoints

- Incidence of TEAEs and the AESI (orthostatic hypotension) in the Extension Phase
- Concomitant medication use in the Extension Phase
- Change from Trial Baseline in vital signs in the Extension Phase
- Change from Trial Baseline in 12-lead ECG measurements in the Extension Phase
- Change from Trial Baseline in clinical safety laboratory test results in the Extension Phase

# 9.6.2.1.3 Exploratory Endpoints

- Change from both Baselines in proportion of subjects with decline in FVC % predicted ≥10% at Week 104
- Change from both Baselines in the 6MWT results to Week 104
- Change from both Baselines in K-BILD scores to Week 104
- Change from both Baselines in L-IPF scores to Week 104
- Change from both Baselines in LCQ scores to Week 104
- Time to first hospitalization due to respiratory distress from fipaxalparant (HZN-825) Baseline up to Week 104
- Time to first onset of the composite endpoint of PFS from fipaxalparant (HZN-825) Baseline up to Week 104, where progression includes decline in FVC % predicted ≥10% from Baseline or death
- •
- •

 Time to death due to respiratory deterioration from fipaxalparant (HZN-825) Baseline up to Week 104

# 9.6.2.1.4 Exploratory PK Endpoints

• Pre- and post-dose concentrations of fipaxalparant (HZN-825) in the Extension Phase

# 9.6.2.2 Analysis Sets

Three analysis sets will be defined for the Extension Phase of the trial.

- The FAS will include all subjects who entered and received at least 1 dose or partial dose of fipaxalparant (HZN-825) in the Extension Phase. This will be the analysis set used for efficacy data analyses; subjects will be analyzed according to the treatment group to which they were randomized in the Core Phase and combined into an 'overall' group.
- The safety analysis set will include all subjects who receive at least 1 dose or partial dose of fipaxalparant (HZN-825) in the Extension Phase. Subjects in this analysis set will be

Fipaxalparant (HZN-825) Protocol: HZNP-HZN-825-303 Version 5.0, Amendment 4

analyzed according to the group determined by the treatment the subject received in the Core Phase and combined into an 'overall' group.

• The PK analysis set will include all subjects who received at least 1 dose or partial dose of fipaxalparant (HZN-825) and have at least 1 PK sample post fipaxalparant (HZN-825) treatment in the Extension Phase.

# 9.6.2.3 Efficacy Endpoint Analysis

All efficacy endpoints will be summarized for the FAS using descriptive statistics, presented by the treatment group subjects were randomly assigned to in the Core Phase and overall.

A MMRM will be fit to the data for descriptive purposes using observed change in FVC % predicted values from all planned post-Trial OLE Baseline assessments (Weeks 68, 80, 92, and 104). A similar model that was used in the Core Phase may be used for the Extension Phase. An unstructured covariance matrix will be used for the primary analysis; if the model does not converge, other covariance matrices will be considered. The least squares mean (LS mean) difference in change from OLE Baseline to Week 52 from MMRM will be estimated from this model. For subjects with missing data at 1 or more time points, the available data will be included in the analysis.

Exploratory endpoints will be summarized at each time point. Change from Baseline will be evaluated separately for each of the defined Baselines.

# 9.6.2.4 Safety and Tolerability Analyses

All safety endpoints will be summarized for the safety analysis set in the Extension Phase using descriptive statistics.

The number and percentage of subjects reporting at least 1 TEAE, SAE, AESI and TEAE resulting in premature discontinuation of fipaxalparant (HZN-825) will be summarized by each unique SOC and Preferred Term. AE rates (events per patient-year of follow-up during dosing) will also be summarized to account for the different treatment durations. TEAEs and SAEs will also be summarized by maximum severity and relationship to fipaxalparant (HZN-825), as assessed by the Investigator. Grade 3 and above TEAEs will also be summarized for each unique SOC and Preferred Term.

The number and percentage of subjects using concomitant medications will be summarized by Anatomical Therapeutic Chemical Level 4 term and Preferred Term.

Laboratory values and change from OLE Baseline and fipaxalparant (HZN-825) Baseline will be summarized by visit using descriptive statistics. The laboratory assessment will be categorized as low, normal or high based on normal ranges. Shift tables using categories of low, normal and high from each Baseline to each visit in the Extension Phase will be summarized. If toxicity grading is available, then those grades will also be used for shift table summaries.

Fipaxalparant (HZN-825)
Protocol: HZNP-HZN-825-303
Version 5.0, Amendment 4

Descriptive summaries of observed and change from OLE Baseline and fipaxalparant (HZN-825) Baseline will be presented for each vital sign parameter by visit. A shift table for vital signs by visit will be provided.

ECG results will be summarized for each visit in the Extension Phase.

# 9.6.2.5 Pharmacokinetic Analyses

PK data will be analyzed using the PK analysis set. Plasma concentrations of fipaxalparant (HZN-825) will be summarized descriptively, including arithmetic means, standard deviations, geometric means, coefficients of variation, medians, first and third quartiles and ranges by treatment group in the Core Phase and by time point. Population PK analysis may be performed.

# 9.6.3 Sample Size and Power Considerations

Approximately 135 subjects (45 subjects per treatment group) will be enrolled in the trial. Based on a prior trial of pirfenidone [Nathan et al., 2019] in a similar subject population, change in FVC % predicted is expected to have a standard deviation of 6% to 9% after 52 weeks of treatment. Assuming a clinically important difference between fipaxalparant (HZN-825) and placebo is 3% and a common standard deviation is 9%, a sample size of 45 subjects per treatment group in the Core Phase will provide 85% probability to detect a positive signal (FVC % predicted difference for each dose vs. placebo at Week 52 >1%) and 70% probability to detect a positive signal (FVC % predicted difference for each dose vs. placebo at Week 52 >2%). If the true FVC % predicted difference for each dose versus placebo at Week 52 is 0%, then there is only 15% probability to detect a positive signal (FVC % predicted difference for each dose vs. placebo at Week 52 >2%).

The sample size for the Extension Phase is based on the number of subjects who complete the Core Phase.

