# **Design of the Core Phase of the Trial**

This is a randomized, double-blind, placebo-controlled, repeat-dose, multicenter trial to evaluate the efficacy, safety, and tolerability of fipaxalparant (HZN-825) in subjects with IPF. Subjects will be screened within 8 weeks prior to the Baseline (Day 1) Visit. Approximately 135 subjects who meet the trial eligibility criteria will be randomly assigned in a 1:1:1 ratio on Day 1 to receive fipaxalparant (HZN-825) 300 mg QD, fipaxalparant (HZN-825) 300 mg BID, or placebo for 52 weeks using the following 2 stratification factors:

- 1. Concomitant use of approved IPF therapy (i.e., nintedanib or pirfenidone): yes or no
- 2. FVC % predicted at Baseline: ≥70% or <70%

The Core Phase will include up to an 8-week Screening Period and a 52-week Double-blind Treatment Period. Subjects will take their first dose of trial drug at the clinic on Day 1 (Week 0) and will participate in trial visits at Week 4 and every 6 weeks thereafter until Week 52. Subjects who complete the 52-week Double-blind Treatment Period may be eligible to enroll into the Extension Phase of the trial. If the subject does not enroll into the Extension Phase, a Safety Follow-up Visit will occur 4 weeks after the last dose of trial drug.

If a subject prematurely discontinues trial drug, he/she will be asked to remain in the trial, participating in the scheduled trial visits through Week 52. If a subject prematurely discontinues trial drug and does not wish to continue in the trial, he/she will be asked to return for a clinic visit and undergo the Week 52 assessments.

An interim analysis with a futility analysis will be performed

These unblinded efficacy and safety data will be provided to an independent data monitoring committee (IDMC) and will be used to inform conduct of the current trial. The IDMC will include at least 1 statistician and at least 2 clinicians experienced in clinical trials and managing IPF subjects. The IDMC charter will include processes to unblind select Horizon personnel who are not directly involved with the trial conduct to assess unforeseen issues.

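### The sample-size section gives correct signal probabilities for 1- and 2-point bars that no visible analysis uses, omits the power of the planned test (about 47% for BID at SD 9, 77% at SD 6), and does not support the beta of 0.150 in SAP 2.1.1

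*Protocol*

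**What the plan says.** Protocol 9.6.3 states: "Approximately 135 subjects (45 subjects per treatment group) will be enrolled in the trial". From a prior pirfenidone trial, "change in FVC % predicted is expected to have a standard deviation of 6% to 9% after 52 weeks of treatment". With a true difference of 3 points and a common SD of 9, the section says that 45 per arm "will provide 85% probability to detect a positive signal", where a signal is an observed difference from placebo above 1 point at Week 52, and it gives 70% for a bar of 2 points. If the true difference is zero, "then there is only 15% probability to detect a positive signal", and here the bar is 2 points. The synopsis and SAP 1.3 repeat the paragraph. None of the three gives the power of a hypothesis test or a false-signal rate for the 1-point bar.

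The primary decision rule is different. Protocol 9.6.1.9 and SAP 3.4 set an overall two-sided alpha of 0.10 and a fixed order: "the BID dose will be tested versus placebo first; if significant, the QD dose will then be tested". Both doses must succeed before the key secondary endpoint is tested. The tipping-point analysis in protocol 9.6.1.3 likewise takes p≤0.10 as the conclusion to be overturned.

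At the interim, protocol 9.6.1.8 and SAP 2.1 stop for futility if conditional power is below 10% for both doses. SAP 2.1.1 computes conditional power under the current trend and under a hypothesized trend, the latter with alpha 0.10, beta 0.150 and information fraction 0.5.

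**The concern.** The section's title mentions power, but its figures describe a criterion on the point estimate. The trial's conclusion will be drawn from a p-value, so the paragraph does not tell the reader how likely the trial is to reach its primary conclusion under the assumed effect.

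The paragraph also puts the true-signal rate of the lenient bar (85%) near a false-signal rate for the stricter one (15%). Read quickly, the two look like a matched pair.

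The beta in SAP 2.1.1 matters for a different reason. With alpha 0.10 it fixes the hypothesized drift at the value that gives the significance test 85% power. If the design does not supply that drift, conditional power under the hypothesized trend is too optimistic, and the IDMC would see a more encouraging number than the design assumptions justify.

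**Working it through.** **Inputs.** 45 per arm, true difference 3, SD 9 (range 6 to 9), from protocol 9.6.3. Two-sided alpha 0.10 and the BID-then-QD order, from protocol 9.6.1.9. Beta 0.150 and t = 0.5, from SAP 2.1.1. The observed difference is treated as normal, in a plain two-arm comparison at Week 52.

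**Step 1: the plan's own figures.** SE = 9 × √(2/45) = 1.897.
- P(observed >1 | true 3) = Φ(2/1.897) = 85.4%
- P(observed >2 | true 3) = Φ(1/1.897) = 70.1%
- P(observed >2 | true 0) = 1 − Φ(2/1.897) = 14.6%

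All three reproduce the stated 85%, 70% and 15%.

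**Step 2: the missing false-signal rate.** P(observed >1 | true 0) = 1 − Φ(1/1.897) = 29.9% per dose. At SD 6, SE = 6 × √(2/45) = 1.265 and the rate is 21.5%.

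**Step 3: power of the planned test.** Power for BID = Φ(3/SE − 1.645).
- SD 9: Φ(1.581 − 1.645) = 47.5% (47.0% with the t distribution).
- SD 6: Φ(2.372 − 1.645) = 76.6%.
- SDs of 8 and 7 give 55.3% and 65.1%.

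At SD 9 the smallest significant observed difference is 1.645 × 1.897 = 3.12 points, slightly more than the assumed effect.

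If both doses truly differ from placebo by 3 points, both are significant with probability 31% at SD 9 and 64% at SD 6. These two figures come from simulation with a shared placebo arm.

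**Step 4: the beta in SAP 2.1.1.** The hypothesized drift there is 1.645 + 1.036 = 2.68. The drift implied by the design is 3/SE:
- SD 9: 3/1.897 = 1.58
- SD 6: 3/1.265 = 2.37

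No SD in the stated range gives 2.68. At SD 9, beta 0.150 needs a true difference of 2.681 × 1.897 = 5.1 points. For a 3-point difference it needs an SD of 3/(2.681 × √(2/45)) = 5.3.

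**Step 5: effect on the hypothesized-trend formula.** With t = 0.5 the argument is (0.707·Z + 0.5·drift − 1.645)/0.707.
- At interim Z = 0 and drift 2.68: (1.341 − 1.645)/0.707 = −0.43, so conditional power is 33%.
- At interim Z = 0 and drift 1.58: (0.791 − 1.645)/0.707 = −1.21, so conditional power is 11%.
- Conditional power of 10% requires an argument of −1.28. That occurs at about Z = −0.85 with drift 2.68 and about Z = −0.07 with drift 1.58.

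**The case against.** The strongest reply is that nothing in 9.6.3 is miscalculated or mislabelled. Each probability is printed with its bar and called the chance of a positive signal, not power. Sizing a Phase 2b trial on a point-estimate criterion is a legitimate choice, and the change was open: the protocol's amendment summary shows a power statement for 360 subjects being replaced when enrolment was cut to 135. All of this stands, so the defect is not arithmetic. The section speaks of each dose, so leaving out the chance that at least one dose looks positive is not an error either.

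A reader might infer that no analysis anywhere uses the bars. The documents do not support that. The interim text is partly redacted, the IDMC charter is not available, and protocol 9.6.1.8 allows other statistics for futility and dose selection. The claim holds for the visible text only. There, the phrase positive signal recurs only for Week 28 in standard-of-care subjects, without a number.

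A reader might also infer that the 85% of 9.6.3 was carried into SAP 2.1.1 as beta 0.150. The digits match, but the SAP gives no source, so the link is unproven. What stands without it is that 0.150 does not agree with 3 points and 45 per arm at any SD from 6 to 9.

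Finally, the visible text does not say which trend drives the 10% rule. If it is the current trend, beta has no effect on futility, and the discrepancy affects only the second conditional power figure shown to the IDMC.

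**Conclusion.** The point holds as a gap in the stated operating characteristics and an inconsistency in one interim constant. The plan does not report the power of its own primary test: about 47% for BID and 31% for both doses at SD 9, or 77% and 64% at SD 6. It gives no false-signal rate for the bar that carries the 85%: 30% per dose at SD 9, 21% at SD 6. The hypothesized drift of 2.68 in SAP 2.1.1 exceeds the 1.58 to 2.37 that the stated design implies.

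The 47% and 30% must always be quoted with SD 9, which is the top of the stated range. They rest on a two-sample comparison with 45 evaluable subjects per arm. The covariates in the mixed model could lower the residual SD and raise power; missing data would lower it. With dropout assumed at 10% or 20% (the sample-size section makes no allowance), power at SD 9 would be 44% or 41%.

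It would be tempting to conclude that the trial is too small. The documents do not support that: the sponsor chose a signal-finding size, and modest power for a formal test is not in itself an error in a Phase 2b trial.

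**What to change.** 1. In protocol 9.6.3, the synopsis and SAP 1.3, add the power of the planned two-sided 0.10 test for BID and for both doses, each with its SD. Beside each true-signal rate, give the false-signal rate for the same bar (at SD 9, 85% with 30% for the 1-point bar and 70% with 15% for the 2-point bar).
2. In SAP 2.1.1, derive the hypothesized drift from the stated design (1.58 for 3 points, SD 9 and 45 per arm), or state the effect and SD that justify beta 0.150.
3. In SAP 2.1, say which trend governs the 10% futility rule.

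The first change is wording only, and its cost is that the stated figures look less favourable. The second can be more than a change of constant. If the hypothesized trend governs, the 10% threshold moves from about Z = −0.85 to about Z = −0.07, which makes stopping for futility easier. It should therefore be decided together with the third. No change in sample size is needed.
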